9.3. Study Drug Administration

Cohorts 1 and 2

Subjects will take study drug capsule(s) by mouth at approximately 2200 hours for 14 consecutive days beginning on Day 1. Each dose of study drug is to be administered with a bottle of vanilla-flavored (~237 mL); subjects should finish consuming the entire bottle of within 30 minutes of taking study drug. The designated NBI-74788 dose (50 or 100 mg) will be administered as 1 or 2 NBI-74788 50 mg capsules.

Cohort 3

Subjects will take study drug capsules by mouth at approximately 1900 hours for 14 consecutive days beginning on Day 1. Each dose of study drug is to be administered with their evening meal; subjects should complete their evening meal within 30 minutes of taking study drug. The designated NBI-74788 dose (100 mg) will be administered as 2 NBI-74788 50 mg capsules.

Cohort 4

Subjects will take study drug capsules by mouth for 14 consecutive days beginning at approximately 1900 hours on Day 1; subsequently, study drug will be taken at approximately 0700 hours (with breakfast) and approximately 1900 hours (with evening meal). Subjects should complete their respective meals within 30 minutes of taking study drug. The designated NBI-74788 dose (100 mg) will be administered as 2 NBI-74788 50 mg capsules (200 mg total daily dose).

9.4. Study Drug Storage and Return

NBI-74788

and in a locked area accessible only to the pharmacist or designee until dispensing.

Study drug should be stored and inventoried according to applicable state and federal regulations and study procedures.

Written documentation to account for study drug and study drug materials is mandatory; all unused study drug and study drug materials must be kept in a secure location for final accountability and reconciliation. Returned study drug and study drug material must be accounted for on a study drug return form provided by NBI or the designee. The investigator must provide a written explanation for any destroyed or missing study drug or study drug materials.

Returns will be shipped to NBI or its designee at the completion of the study according to instructions provided by NBI or its designee. Study drug return forms must be completed for the shipment of returns and sent with the study drug and study drug materials. One copy of the study drug return form will be retained in the investigator's study file. All returned study drug and study drug materials should be stored, inventoried, reconciled, and returned according to applicable state and federal regulations and study procedures.

9.5. Blinding

This is an open-label study.

9.6. Study Compliance and Accountability

All doses of the study drug ingested in the study center will be taken in the presence of study site personnel who will check the subject's hands and mouth to confirm that the dose has been swallowed.

The quantity of study drug dispensed, used, and returned will be recorded on a dispensing log or otherwise documented. The quantity of study drug lost or destroyed, must also be accounted for

and documented. The designated pharmacist or qualified personnel will be responsible for maintaining accurate records of the quantity and dates of all study drug supplies received, dispensed, and returned.

The exact time of medication dosing will be recorded on the eCRF.

10. ADVERSE EVENTS

All AEs, whether observed by the investigator, reported by the subject, noted from laboratory findings, or by other means, will be recorded from the time the subject has signed the ICF until the subject's final study visit.

10.1. Definition

An AE is any untoward medical occurrence associated with the use of a drug in humans, whether or not considered drug related. During the study, clinically significant adverse changes in clinical status, ECGs, laboratory values (not associated with an AE or concurrent medical condition), or physical examinations are considered AEs. Any subject complaint associated with such an abnormal finding will also be reported as an AE.

AEs include, but are not limited to: (1) a worsening or change in nature, severity, or frequency of conditions present at the start of the study; (2) subject deterioration due to primary illness; (3) intercurrent illness; and (4) drug interaction.

All suicidal behaviors and clinically significant suicidal ideations will be documented as an AE.

Subjects should be questioned in a general way, without asking about the occurrence of any specific symptom. The investigator should attempt to establish a diagnosis of the event based on signs, symptoms, and/or other clinical information. In such cases, the diagnosis should be documented as the AE and not the individual signs/symptoms. Following questioning and evaluation, all AEs, whether believed by the investigator to be related or unrelated to the study drug, must be documented in the subject's medical records, in accordance with the investigator's normal clinical practice and on the AE eCRF. Each AE is to be evaluated for duration, intensity, frequency, seriousness, outcome, other actions taken, and relationship to the study drug.

The following are not considered AEs:

- Continuous persistent disease/symptom present before drug administration, unless it unexpectedly progresses, or increases in severity following drug administration.
- Pregnancy.

10.2. Intensity of Adverse Events

AEs must be graded for intensity. An intensity category of mild, moderate, or severe, as defined in Table 4, must be entered on the AE eCRF. It should be noted that the term "severe" used to grade intensity is not synonymous with the term "serious."

Grade	Intensity
Mild	An AE that is usually transient and may require only minimal treatment or
	therapeutic intervention. The event does not generally interfere with usual activities
	of daily living.
Moderate	An AE that is usually alleviated with additional specific therapeutic intervention.
	The event interferes with usual activities of daily living, causing discomfort but
	poses no significant or permanent risk of harm to the research participant.
Severe	An AE that interrupts usual activities of daily living, or significantly affects clinical
	status, or may require intensive therapeutic intervention.

Table 4:Intensity of Adverse Events

10.3. Relationship to Study Drug

The investigator will document his/her opinion of the relationship of the AE to treatment with study drug using the criteria outlined in Table 5. An AE is deemed associated with the use of the study drug "if there is a reasonable possibility that the drug caused the AE" (otherwise referred to as a suspected adverse reaction). Reasonable possibility means there is evidence to suggest a causal relationship between the drug and the AE (Title 21 CFR 312.32 [a]).

Table 5:	Relationship of Adverse Events to Study Drug
----------	--

Relationship	Description
Definite	A reaction that follows a reasonable temporal sequence from administration of the drug or in
	which the drug level has been established in body fluids or tissue; that follows a known or
	expected response pattern to the suspected drug; and that is confirmed by improvement on
	exposure.
Possible	An AE in which there is reasonable possibility that the drug caused the event. Reasonable possibility means there is evidence to suggest a causal relationship between the drug and the AE.
Unlikely	A reaction that follows a reasonable temporal sequence from administration of the drug; that
	follows a known or suspected response pattern to the suspected drug; but that could
	reasonably be explained by known characteristics of the subject's clinical state.
Not Related	Any event that does not meet the above criteria.

10.4. Recording Adverse Events

For enrolled subjects, each AE will be listed as a separate entry on an AE eCRF. Screen failure subjects will have AE information noted in the source documentation. The investigator (or designee) will provide information on dates and times of onset and resolution, intensity, seriousness, frequency, action(s) taken, changes in study drug usage, relationship to study drug, and outcome.

The following categories of medical events that could occur during participation in a clinical study must be reported within 24 hours to NBI or its designee:

- SAE, including death (Section 10.6).
- Pregnancy (Section 10.7).

• Events of suicidal behavior or suicidal ideation type 4 (active suicidal ideation with some intent to act, without specific plan) or type 5 (active suicidal ideation with specific plan and intent) based on the C-SSRS.

10.5. Post-Study Follow-Up of Adverse Events

All AEs, including clinically significant changes in ECGs, physical examination findings, or isolated clinically significant laboratory findings must be followed until the event resolves, the condition stabilizes, the event is otherwise explained, or the subject is lost to follow-up. If resolved, a resolution date should be documented on the eCRF.

AEs ongoing at the final study visit (or upon early termination) will be followed for as long as necessary to adequately evaluate the subject's safety or until the event stabilizes or resolves or until the subject is lost to follow up. The investigator is responsible for ensuring that follow-up includes any supplemental investigations as may be indicated to elucidate the nature and/or causality of the AE. This may include additional laboratory tests or investigations, histopathological examinations, or consultation with other health care professionals, as is practical.

10.6. Serious Adverse Events

All SAEs will be recorded from the time the subject has signed the ICF until the final study visit or 30 days after the last dose of study drug, whichever is longer in duration.

10.6.1. Definition of a Serious Adverse Event

An SAE is any AE that results in any of the following outcomes:

- Death.
- A life-threatening AE. Life threatening means that the subject was, in the view of the investigator or Sponsor, at immediate risk of death from the reaction as it occurred. It does not mean that hypothetically the event might have caused death if it occurred in a more serious form.
- Inpatient hospitalization or prolongation of existing hospitalization. Hospitalization for elective treatment or a pre-existing condition that did not worsen during the clinical investigation is not considered an AE. Hospitalization or nursing home admission for the purpose of caregiver respite is not considered an AE. Complications that occur during hospitalization are AEs, and if a complication prolongs hospitalization, the event is considered serious. Treatment in a hospital emergency room is not a hospitalization.
- A persistent or significant incapacity or substantial disruption of a person's ability to conduct normal life functions.
- A congenital anomaly/birth defect.
- Important medical events that may not result in death, be life threatening, or require hospitalization. These events may be considered serious when, based on appropriate medical judgment, they may jeopardize the health of the subject and may require medical or surgical intervention to prevent one of the outcomes listed. Any other event thought by the investigator to be serious should also be reported, following the reporting requirements

detailed in this section. Examples of such medical events include allergic bronchospasm requiring intensive treatment in an emergency room or at home, blood dyscrasias, convulsions that do not result in inpatient hospitalization, or the development of drug dependency or drug abuse.

10.6.2. Managing Serious Adverse Events

Subjects experiencing an SAE or an emergency situation will be examined by a physician as soon as possible. The physician in attendance will do whatever is medically needed for the safety and well-being of the subject. The subject will remain under observation as long as medically indicated. Appropriate laboratory studies will be conducted until all parameters return to normal or are otherwise explained or stable. The subject will be followed until the SAE resolves or until the subject is medically stabilized. The investigator (or designee) will notify the NBI Medical Monitor (and the IRB, if necessary) immediately (within 24 hours) of the SAE and the outcome of the SAE.

If an investigator becomes aware of an SAE within the time of informed consent until the final study visit or 30 days after the last dose of study drug (whichever is longer in duration), then the event must be documented and reported as described in Section 10.6.3.

10.6.3. Reporting Serious Adverse Events and Other Immediately Reportable Events

Serious AEs and other immediately reportable events (defined in Section 10.4) must be reported within 24 hours of first knowledge of the event by study personnel to the NBI Medical Monitor or NBI Clinical Drug Safety (CDS) Department. Reports of SAEs or pregnancies should be followed by a fax or email of the SAE or Pregnancy Form. It is important that the investigator provide his or her assessment of relationship to study drug at the time of the initial SAE report.

For SAEs or Other Immediately Reportable Events, contact CDS:

10.6.4. Expedited Safety Reports

NBI or its representatives will submit an Expedited Safety Report for any suspected adverse reaction (as defined in Section 10.3) that is considered both serious and unexpected within 15 calendar days and for any unexpected fatal or life threatening experience within 7 calendar days via telephone or facsimile; or according to country specific regulations.

NBI or its representatives will send copies of each safety report submitted to regulatory authorities to the investigators. The safety report must be submitted to the appropriate IRB as soon as possible. Documentation of the submission to the IRB and receipt by the IRB (if applicable) must be retained for each safety report.

10.7. Pregnancy

Women of childbearing potential will be enrolled in this study. In the event of a pregnancy, the following instructions should be followed.

Pregnancy is neither an AE nor an SAE unless the criteria for an SAE are met. However, all pregnancies in female subjects who received NBI-74788 will be followed to assess for congenital anomaly. If at any time between the time the subject signs the ICF and the last study visit a subject believes she is pregnant, the subject will be instructed to return to the study site within 24 hours and undergo a serum pregnancy test to confirm pregnancy.

All confirmed pregnancies in subjects who received study drug must be immediately reported to NBI (refer to Section 10.6.3 for contact information), followed by fax or email of the pregnancy form to NBI CDS. A first trimester ultrasound will be required for all confirmed pregnancies. Pregnancies in subjects who received NBI-74788 will be followed until resolution (ie, termination [voluntary or spontaneous] or birth).

11. DOCUMENTATION OF DATA

11.1. Case Report Forms

The case report form data for this study are being collected with an electronic data capture (EDC) system for the study-specific eCRFs will comply with Title 21 CFR Part 11. The documentation related to the validation of the EDC system is available through the vendor, for the validation of the study specific eCRFs will be conducted by NBI and the required documentation will be maintained in the Trial Master File.

The investigator will document subject data in his/her own subject files. These subject files will serve as source data for the study. All eCRF data required by this protocol will be recorded by authorized study personnel in the EDC system, with the exception of data captured in an electronic format, which will be loaded electronically into the appropriate eCRFs. All data entered into the eCRF will be supported by source documentation. The eCRF for each subject must be reviewed by the investigator and signed on the appropriate eCRF page(s). This should be done as soon as possible after the subject completes the study.

The investigator or an authorized member of the investigator's staff will make any necessary additions/corrections to the eCRF. All change information, including the date, person performing the corrections, and reason for the change will be available via the electronic audit trail, which is part of the EDC system. The eCRFs will be reviewed periodically for completeness, legibility, and acceptability by NBI (or designee). NBI will also be allowed access to all source documents and medical records pertinent to the study in order to verify eCRF entries. The Principal Investigator will review the eCRFs for completeness and accuracy and enter his or her electronic signature on the eCRFs as evidence thereof.

will provide access to the NBI portal of the EDC system for the duration of the study through a password-protected method of internet access. Such access will be removed from investigator sites at the end of the site's participation in the study. Data from the EDC system will be archived on appropriate data media (CD-ROM, etc.) and provided to the investigator at that time as a durable record of the site's eCRF data. Although not required, the investigator may make paper printouts from that media.

All clinical work conducted under this protocol is subject to GCP regulations. This includes an inspection by NBI and/or health authority representatives at any time. The Principal Investigator will agree to the inspection of study-related records by health authority representatives and/or NBI.

11.2. Data Capture, Review, and Validation

Data entered in the EDC system will be verified against the source data by NBI (or designee). Any discrepancies will be corrected on-line by authorized site personnel. After completion of the entry process, automated (computer-generated) logic checks will run in order to identify items such as inconsistent study dates. In addition, manual review/checks may be conducted by NBI on the data. Any inconsistencies/errors/omissions identified will be sent to the site (via an electronic query) for the necessary corrections to be made to the eCRF. Once entered and saved in an eCRF, data immediately become part of the study database and are available to NBI.

11.3. Coding Dictionaries

AEs and medical history will be coded using the chosen version of the Medical Dictionary for Regulatory Activities (MedDRA). Prior and concomitant medications will be coded using the chosen version of the World Health Organization Drug Dictionary (WHODrug).

12. STATISTICAL AND ANALYTICAL PLAN

Descriptive statistical methods will be used to summarize the data from this study. The term "descriptive statistics" refers to the number of subjects (n), mean, median, standard deviation (SD), standard error of the mean (SEM), minimum, and maximum for continuous variables, and refers to the number of subjects (or events) and percentage for categorical variables. Confidence intervals may be presented for selected variables as well. Summary statistics will be presented by dose cohort unless stated otherwise.

12.1. Analysis Sets

Data summaries for this study will be based on the safety analysis set, which will include all subjects who receive a dose of study drug.

12.2. Sample Size

The sample size for this study is based on practical clinical considerations with no formal statistical power calculations.

12.3. Handling of Missing Data

All available study data will be included in relevant summaries and data displays, including any available data for subjects with incomplete or missing data.

12.4. Disposition of Subjects

A summary of subject disposition will be prepared that displays the number of subjects who were enrolled, received study drug, and completed the study. The number of subjects who did not complete the study will be displayed both overall and by reason for discontinuation.

12.5. Demographics and Baseline Characteristics

Age, height, weight, BMI, gender, race, ethnic group, **17**-OHP levels will be summarized with descriptive statistics.

12.6. Pharmacokinetic Data

Descriptive statistics and graphical displays will be presented for NBI-74788 and metabolites plasma concentrations by dose cohort and scheduled sampling time. For these summaries, values that are below the limit of quantitation (BLQ) will be set equal to zero.

Individual subject plasma concentration vs. time plots will also be presented.

The following plasma PK parameters will be calculated for NBI-74788 and metabolites using noncompartmental methods and summarized by dose cohort using descriptive statistics:

- Area under the plasma concentration versus time curve from 0 hours to last measurable concentration (AUC_{0-tlast})
- Area under the plasma concentration versus time curve from 0 to 24 hours (AUC₀₋₂₄) (Cohorts 1, 2, and 3)
- Area under the plasma concentration versus time curve from 0 to 12 hours (AUC₀₋₁₂) (Cohort 4)
- Maximum plasma concentration (C_{max})
- Time to maximum plasma concentration (t_{max})
- Delay time between time of dosing and time of appearance of measurable test article (T_{lag})
- Terminal half-life $(t_{\frac{1}{2}})$
- Apparent terminal rate constant (λz)
- Apparent mean residence time (MRT)

Additional PK parameters for Day 14 only:

- Average plasma concentration at steady state (C_{avg})
- Percent fluctuation at steady state (%fluctuation)
- Accumulation index at steady state

• Apparent systemic clearance after oral administration (CL/F) (NBI-74788 only)

12.7. Pharmacodynamic Data

The primary PD assessments are: morning 17-OHP (serum; ng/dL) from the 0600, 0800, and 1000 hour samples (8-, 10-, and 12-hour postdose samples from Cohorts 1 and 2 and 11-, 13-, and 15-hour postdose samples from Cohorts 3 and 4). Secondary PD assessments are: 17-OHP at all other times, androstenedione (serum; ng/dL), testosterone (serum; ng/dL), cortisol (serum; μ g/dL), and ACTH (plasma; pg/mL).

The PD assessments listed above will be summarized with descriptive statistics (including change from predose) and in graphical displays by dose cohort and timepoint.

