6. STUDY DESIGN

6.1. Overview of Study Design

This is a Phase 2, open-label, multiple-dose, dose-escalation study to assess the safety, tolerability, PK, and PD of NBI-74788 in approximately 30 adult female and male subjects (18 to 50 years of age) with a documented medical diagnosis of classic 21-hydroxylase

deficiency CAH. The study will include a sequential-cohort design with 4 NBI-74788 dosing regimens, with each regimen administered for 14 consecutive days:

- Cohort 1: NBI-74788 50 mg once daily with a bottle of vanilla-flavored (~237 mL) at approximately 2200 hours.
- Cohort 2: NBI-74788 100 mg once daily with a bottle of vanilla-flavored (~237 mL) at approximately 2200 hours.
- Cohort 3: NBI-74788 100 mg once daily with the evening meal at approximately 1900 hours.
- Cohort 4: NBI-74788 100 mg twice daily with breakfast at approximately 0700 hours and with the evening meal at approximately 1900 hours.

There will be an approximate 2-week period to evaluate safety and tolerability data before proceeding from Cohort 1 to Cohort 2. Subjects who previously completed the current study in Cohort 1 or Cohort 2 may reenroll to participate in Cohorts 3 or 4 (in addition to new subjects).

Table 1 depicts the cohorts, doses, and number of subjects per cohort.

Cohort	NBI-74788 Dose	Approximate Dosing Time(s)	Number of Subjects
1	50 mg	2200 hours	8-10
2	100 mg	2200 hours	8-10
3	100 mg	1900 hours	8-10
4	100 mg	0700 and 1900 hours	Up to 8

Table 1:Dose Cohorts, Doses, and Number of Subjects

Subjects must provide informed consent prior to any study-related procedures. Subjects will then be screened for eligibility to participate in the study for up to approximately 3 weeks (Days -28 to -8). Subjects who reenroll and have had a stable medication regimen for CAH since their last visit in this study do not have to undergo screening; those who reenroll and have had a change to their medication regimen for CAH must undergo a second screening visit. During screening, subjects will provide a single blood sample in the morning between 0700 and 1000 hours (prior to first morning dose of hydrocortisone) to determine their 17-OHP levels for study entry.

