6.2. Dose Escalation Procedure

Cohort 1 will consist of approximately 8 to 10 subjects who will receive a daily dose of NBI-74788 50 mg at approximately 2200 hours for 14 days (subjects will receive study drug at the site on Days 1, 2, and 14, and self-administer study drug at home on Days 3 to 13). Following the completion of Day 15 assessments for all subjects in Cohort 1, a medical monitor will review the accumulated safety and tolerability results to ensure there are no safety concerns with proceeding to the 100 mg dose (Cohorts 2 and 3), and to determine if a maximum tolerated dose (MTD) has been reached. If the MTD is reached, no dose escalation will occur. There will be an approximate 2-week period between Cohorts 1 and 2 to accommodate this safety review. A similar procedure will be used prior to proceeding to the 100 mg twice daily dose (Cohort 4).

If the medical monitor determines that it is safe to proceed to NBI-74788 100 mg, subjects in Cohort 2 will be administered NBI-74788 100 mg daily for 14 days. Dosing for Cohorts 3 and 4 may begin simultaneously with Cohort 2.

During the 14-day dosing period for any cohort, dosing may be postponed or halted if one or more subjects experience a severe or serious adverse event (AE), or if the type, frequency, or severity of AEs becomes unacceptable. If dosing is postponed, the medical monitor will review all available safety, tolerability, and PK data before allowing any further subjects to receive study drug.

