7.4. Randomization

This is a single-arm study.

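### Testosterone is summarised by cohort with women and men pooled; if male levels are several times female levels, the pooled means and absolute changes mainly reflect the men and each cohort's sex mix.

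*Combined protocol and SAP*

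**What the plan says.** Section 12.7 makes morning 17-OHP the primary PD assessment and continues: "Secondary PD assessments are: 17-OHP at all other times, androstenedione (serum; ng/dL), testosterone (serum; ng/dL"), with cortisol and ACTH completing the list. It then fixes the presentation for all of them: "The PD assessments listed above will be summarized with descriptive statistics (including change from predose) and in graphical displays by dose cohort and timepoint". The default in the opening paragraph of Section 12 is the same: "Summary statistics will be presented by dose cohort unless stated otherwise". For continuous variables, descriptive statistics there "refers to the number of subjects (n), mean, median, standard deviation (SD), standard error of the mean (SEM), minimum, and maximum for continuous variables".

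No section states a split of testosterone by sex. Section 12.6 promises individual concentration plots for PK; Section 12.7 promises none for PD. Section 12.5 summarises sex as a baseline characteristic.

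Section 6.1 enrols "approximately 30 adult female and male subjects (18 to 50 years of age"), with no quota by sex. On cohort size, Section 6.2 says "Cohort 1 will consist of approximately 8 to 10 subjects". Table 1 gives the same range for Cohorts 2 and 3, and up to 8 for Cohort 4. On randomisation, Section 7.4 says only: "This is a single-arm study". Section 5 makes the effect of different regimens on PD biomarkers an objective, and Section 6.1 lets completers of Cohorts 1 and 2 re-enrol in Cohorts 3 or 4.

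**The concern.** Pooling by sex is a stated choice here, not a missing detail. A mean in ng/dL over two groups on different scales describes neither group, and the group with the larger values dominates both the mean and its standard error. A fall in women's testosterone could then be hard to see. Two regimens could also look different because one cohort happened to contain more men.

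This matters because Section 4.1 gives normalising androgen production as the rationale for the drug and names testosterone among the overproduced steroids. The regimen objective also invites readers to compare cohorts. The planned median, minimum and maximum do not separate a mixture of two groups. The baseline table would show an imbalance in sex without removing its effect on the marker.

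**Working it through.** The plan gives no power, effect size or SD for testosterone, so there is no figure to reproduce. The documents supply the grouping, the statistics shown and the cohort sizes. Levels by sex, sex mix, variability and size of effect are all **assumed** below.

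**1. Pooled baseline, n = 8.** Assumed means are 30-50 ng/dL (women) and 300-600 ng/dL (men). With f women and m men, pooled mean = (f × women's mean + m × men's mean)/8.
- 6 women: (6×30 + 2×300)/8 = 97.5 to (6×50 + 2×600)/8 = 187.5.
- 2 women: (2×30 + 6×300)/8 = 232.5 to (2×50 + 6×600)/8 = 462.5.

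**2. Pooled change against its SEM.** Women fall by 25 (SD 15); men average 0 (SD 80). Pooled variance = (f×15² + m×80²)/8 + (f/8)(m/8)×25².
- 6 women: mean -18.75; variance 1768.75 + 117.19 = 1885.94; SEM = 43.43/√8 = 15.35; ratio **-1.2**. Women alone: -25/(15/√6) = **-4.1**.
- 2 women: mean -6.25; variance 4856.25 + 117.19 = 4973.44; SEM = 70.52/√8 = 24.93; ratio **-0.25**. Women alone: -25/(15/√2) = **-2.4**, on 1 degree of freedom.

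No change in men is the case of greatest dilution among those where men do not rise. If men also fall by 25 ng/dL, the between-sex term vanishes. The ratios become -25/(√1768.75/√8) = -1.7 and -25/(√4856.25/√8) = -1.0.

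**3. Dependence on the male-to-female ratio R.** Set the female level to 1 and the male level to R. Women fall by half and men are unchanged, so the pooled percent change is -50 × f/(f + mR). The last two columns give mean change/SE with 4 men of 8, using within-sex variation only (SD of change = CV × √2 × level).

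| R | 2 men of 8 | 4 of 8 | 6 of 8 | Change/SE, CV 15% | Change/SE, CV 30% |
|---|---|---|---|---|---|
| 1 | -37.5% | -25% | -12.5% | -3.3 | -1.7 |
| 2 | -30% | -16.7% | -7.1% | -2.1 | -1.05 |
| 5 | -18.8% | -8.3% | -3.1% | -0.9 | -0.46 |
| 10 | -11.5% | -4.5% | -1.6% | -0.5 | -0.23 |
| 15 | -8.3% | -3.1% | -1.1% | -0.3 | -0.16 |

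For the four women alone the ratio is -4.7 (CV 15%) or -2.4 (CV 30%) at every R.

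**4. Sex mix and observed levels.** With no drug effect, going from 4 to 2 men of 8 moves the mean from (4 + 4R)/8 to (6 + 2R)/8. That is a drop of 17%, 33%, 41% or 44% at R = 2, 5, 10 or 15. If half of eligible subjects are men, two independent cohorts of equal size differ by at least 2 men with probability 0.45 (n = 8) or 0.50 (n = 10).

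**5. Sex mix and change from predose.** With no drug effect the expected change is zero whatever the mix. With the same 30% fall in both sexes, the absolute change with 6 men of 8, relative to that with 2, is (6R + 2)/(2R + 6) = 1.4, 2.0, 2.4 or 2.6 at R = 2, 5, 10 or 15.

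**The case against.** The strongest reply is that the size of the problem rests wholly on assumed levels and that the plan already contains a partial remedy. Much of this stands.

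- A reader might infer that men's values will hide any change in women. The documents do not support that. It needs a high ratio, enough men, and men who respond little. At R of 1-2 with CV 15%, half men still leaves 3.3 and 2.1 SE. If both sexes fall by the same proportion, the pooled mean falls by that proportion too.
- A reader might infer that differences between cohorts merely track the sex mix. The planned change from predose removes the pure level shift when the drug has no effect. What remains is that a proportional effect, expressed in ng/dL, grows with the share of men.
- A reader might take the background as evidence that androgen excess has separate consequences in each sex. Section 4.1 links androgens to virilisation in females but links the male complication to ACTH. It says nothing about testosterone levels by sex.
- The fall of 25 ng/dL is large, at 50-83% of the assumed female means. The women-only ratio of -2.4 comes from two women (p about 0.26; 95% interval about -25 ± 135 ng/dL), so it does not show that a split would reveal an effect.
- Testosterone is one of several secondary markers, no between-cohort test is planned, and a split could be produced later because sex is recorded.

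None of this makes the pooled mean interpretable when the scales differ.

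**Conclusion.** The point holds conditionally. The pooled grouping is stated in Section 12.7, no other section separates the sexes, and nothing balances sex across cohorts of about 8-10. If male levels are about five or more times female levels and half a cohort is male, a halving in women with no change in men appears as a pooled fall of about 8% or less. That is under 1 SE even at CV 15%. In the same range (R = 5-15), an identical proportional effect looks 2.0-2.6 times larger in ng/dL with 6 men of 8 than with 2.

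These sizes rest on the assumed ratio, sex mix, variability and male response. At a ratio near 1-2 the effect in women is diluted, not lost. The harm is to the descriptive reading of one secondary PD marker. No error rate is involved, and the primary morning 17-OHP assessment is unaffected.

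**What to change.** In Section 12.7, state that testosterone will be summarised and plotted by sex within dose cohort and timepoint. Show observed values, change, and percent change or ratio to baseline. Because cells will hold about 2-6 subjects, show individual values as well.

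Counts of women and men by cohort need no addition, since Section 12.5 read with the by-cohort default in Section 12 already provides them. Any summary of women across cohorts should be labelled supportive, because it mixes four regimens. It should also account for subjects who re-enrol, so that one woman is not counted twice as if independent.

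The cost is a sentence or two of text and one extra table split, with no new data. The downside is small cells, so the by-sex results should be read as description.
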